6.4.2 Safety

Adverse events will be classified according to two definitions:

- Reported during the dietary lead-in period
- Treatment emergent. This is further categorised as:
- Ongoing from the dietary lead-in period and subsequently worsening during the randomised period, and
- Starting during the randomised period. Any adverse events starting/worsening up to 30 days after the last dose of study medication will be classified as treatment emergent.

Any reported adverse event that starts/worsens more than 30 days after last dose of study medication will not be classified as treatment emergent.

The incidence of adverse events will be categorised by system organ class and preferred term according to the National Medical Terminology Officially Accepted and will be tabulated by treatment/dose.

Clinical chemistry, vital signs, physical exam, other urinalysis data, and other safety data will be summarised using descriptive statistics.

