Initially a Friedman analysis will be performed, then, for comparing basal state against 8 week, inside each group, a Willcoxon test will be performed. For comparing each one of Rosuvastatin groups against placebo group at week 8 a U Man Whitney test will be done. Also, the percentage of reduction –week 8 minus basal- obtained in the placebo group will be contrasted against the percentage of reduction in each one of the Rosuvastatin groups using a U Man Whitney test. In all the cases a p < 0.05 will be considered significant.

Lipids (other than TGs), apolipoproteins and hsCRP comprising secondary endpoint (1, 2 and 3) will be analysed in a similar way.

Adverse events can occur in the dietary lead-in phase and/or the randomised phase of the study. The latter phase will include the period up to 30 days after the last dose of study medication. All adverse events will be classified according to the following:

- Reported during the dietary lead-in period
- Treatment emergent. This is further categorized as:
 - Ongoing from the dietary lead-in period and subsequently worsening during the randomised period, and
 - Starting during the randomized period.

All adverse events will be categorized by the body system and preferred term assigned to the event using National Medical Terminology Officially Accepted terms and listed for each subject. For subjects in the dietary lead-in safety population events occurring during the dietary lead-in phase will be summarised by frequency; in the randomized safety population treatment emergent events will be reported as frequencies in each treatment group. Frequencies of adverse events leading to withdrawal from the randomized period will also be tabulated and reported by treatment group. Adverse events leading to death, serious adverse events and drug related adverse events would be presented similarly.

TABLE OF CONTENTS

PAGE

	TITLE PAGE	1
	PROTOCOL SYNOPSIS	2
	TABLE OF CONTENTS	6
	LIST OF ABBREVIATIONS AND DEFINITION OF TERMS	10
1.	INTRODUCTION	13
1.1	Background	13
1.2	Rationale for this study	14
2.	STUDY OBJECTIVES	14
2.1	Primary objective	14
2.2	Secondary objectives	14
3.	STUDY PLAN AND PROCEDURES	
3.1	Overall study design and flow chart	15
3.2	Rationale and risk/benefit assessment	20
3.2.1	Rationale for study design and control group	
3.2.2	Risk/benefit and ethical assessment	
3.3	Selection of study population	
3.3.1 3.3.2	Study selection record Inclusion criteria	
3.3.3	Exclusion criteria	
3.3.4	Restrictions	

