Visit window allowed is ± 2 day. During this visit, laboratory results of the prior visit will be available and patients fulfilling the inclusion criterion will be randomised.

- 1. Fasting TG \geq 200 mg/dL and < 800mg/dL from visit 2.
- 2. Fasting LDL-C \geq 100mg/dL and \leq 190 mg/dL at visit 2.
- 3. Record of adverse events
- 4. Study drug will be dispensed in this visit.
- 5. Record of concomitant medication

[figure not shown]
Visit 3. Final (Week 8)

Visit window allowed is ± 3 days. Visit 3 will occurred after 8 weeks of following patients with treatment. This will be the final visit.

- 1. TLC advisory
- 2. Complete physical examination including anthropometrics and vital signs
- 3. Laboratory samples (see table 1)
- 4. Record of adverse events
- 5. Record of concomitant medication
- 6. Study drug will be recovered in this visit. Tablets will be counted and noted for assessing compliance.
- 7. All patients will be offered the opportunity to continue with active commercially available therapy with rosuvastatin, according to the expert opinion of investigator, once the protocol is complete.

Clinical Study Protocol Drug Substance Rosuvastatin Study Code DM-CRESTOR-0002 Edition Number 2.1 Date 28-March-2007

Figure 1 Study flow chart

RSV: rosuvastatin

Clinical Study Protocol Drug Substance Rosuvastatin Study Code DM-CRESTOR-0002 Edition Number 2.1 Date 28-March-2007

Table 1 **Study Plan**

Week	-5	-1	0	8
Visit	1	2	2.1 ⁿ	3
Visit window		± 3 days	±2 day	± 3 days
Informed consent ^a	✓			
Dietary counselling	✓		✓	✓
24 hrs diet recall	✓		✓	✓
Medical history/demography	✓			
Concomitant medication	✓ b	✓	✓	✓
Physical examination ^c	✓ ^d	✓		✓
Vital signs	✓	✓		✓
Eligibility criteria ^e	✓	✓	✓	
Randomization			✓	
Fasting lipid profile ^f	✓	✓		✓
Apolipoproteins ^g		✓		✓
TSH	✓			
Glucose	✓	✓		✓
HbA _{1c}	✓			
Urinalysis ^h		✓		✓
Reduced hepatic profile ^j	✓			
Complete hepatic profile ^k		✓		✓
Urea	✓	✓		✓
Creatinine	✓	✓		✓
СК	✓	✓		✓
β-HCG ¹	✓			
hsCRP		✓		✓
Adverse events ^m		✓	✓	✓
Study drug dispensing			✓	
Study drug compliance and accountability				~

^a Informed consent will be taken at or before Visit 1, before any study related procedures are performed ^b Prior medications to be collected at Visit 1

^c Weight and waist circumference will be measured at Visits 1, 2 and 3. Height will additionally be measured at Visit 1

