4.8.1.2 Recording of adverse events

Adverse events will be identified at all visits except Visit 1 by means of a standard question, "Have you had any health problems since the previous visit?" The patient will be asked to provide a description of the event, the dates of onset and resolution, if any action was taken, the outcome and to assess the intensity of the reported adverse event according to the following scale:

- Mild: awareness of sign or symptom, but easily tolerated
- Moderate: discomfort sufficient to cause interference with normal activities
- Severe: incapacitating, with inability to perform normal activities

The investigator should make a causality assessment of the relationship of the event to the study drug and whether it constitutes an SAE or not (see Appendix B).

If a diagnosis of the patient's condition has been made, then the diagnosis should be recorded as the adverse event (e.g., fever, runny nose, cough can be recorded as "flu"). However, if a diagnosis of the patient's condition has not been made, or only if the individual symptoms are not well recognised, then the individual symptoms should be recorded separately.

It is important to distinguish between serious and severe AEs. Severity is a measure of intensity whereas seriousness is defined by the criteria in Section 4.8.1.1. An AE of severe intensity need not necessarily be considered serious. For example, nausea which persists for several hours may be considered severe nausea, but not a SAE. On the other hand, a stroke which results in only a limited degree of disability may be considered a mild stroke but would be a SAE.

AstraZeneca will classify events using National Medical Terminology Officially Accepted.

For screen failure patients, SAEs should be recorded from the time the patient consents to participate in the study up until the decision is made to discontinue the patient. Non-serious reports are not required for these patients.

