For randomised patients, all adverse events and serious adverse events should be recorded from the time a patient consents to participate in the study up until discontinuation of study treatments. Patients should be instructed to report hospitalisations and any other medically serious events that occur within 30 days after last dosing of study treatment. The investigator should record these and any other serious events he is aware of in the 30-day period following discontinuation of study treatment, on the CRF and should report them to AstraZeneca in the usual manner.

After the initial AE/SAE report, the investigator is required to proactively follow the patient's condition. During the study all AE/SAEs should be followed-up until resolution, or until the condition stabilises and no further change is expected. AstraZeneca reserves the right to ask for further information on any adverse event that may be considered of interest.

Any SAEs ongoing at the final visit or reported within 30 days of study treatment discontinuation should be followed-up until resolution or until stabilised and no further change is expected.

Clinically significant abnormal laboratory values, vital signs or physical examination will not be recorded as adverse events unless:

- SAE criteria is fulfilled
- the patient discontinues the study due to the abnormality
- the investigator considers that the abnormality should be reported as an AE

However, if an abnormal laboratory value/vital sign is associated with clinical signs and symptoms, the sign/symptom should be reported as an AE and the associated laboratory result/vital sign should be considered additional information.

Should a pregnancy occur, it must be reported in accordance with the procedures described in Section 9.4, Procedures in case of pregnancy. Pregnancy in itself is not regarded as an AE unless there is a suspicion that an investigational product may have interfered with the effectiveness of a contraceptive medication.

Should an overdose (accidental or deliberate) occur, it must be reported in accordance with the procedures described in Section 9.3, Procedures in case of overdose, regardless of whether the overdose was associated with any symptom or not. All symptoms associated with the overdose should be reported as AEs.

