6.3 Description of analysis sets

Efficacy

Efficacy data will be evaluated based on the intention-to-treat (ITT) and per-protocol (PP) populations.

The ITT population will consist of randomised patients who have a baseline reading and at least one post-baseline reading for at least one efficacy variable, and who have taken at least one dose of study medication. The PP population will consist of all patients in the ITT population who did not have a major protocol violation or deviations that would be likely to affect the efficacy outcomes (i.e. patients taking lipid lowering therapy other tan study drugs).

Patients will be evaluated using randomised treatment/dose (i.e., rosuvastatin 10 mg, rosuvastatin 20 mg, or placebo) for the ITT efficacy analyses, and actual treatment/dose received for the PP efficacy analyses.

For the test of superiority (versus baseline), the ITT population is the primary analysis population. Analyses of the ITT population will be performed using the last observation carried forward (LOCF) method and also using observed data. The LOCF analysis is the primary analysis. LOCF is defined as the last non-missing post-baseline value for a variable carried forward. If no non-missing value exists after baseline, the value will be treated as missing in the analysis. The analyses will be repeated for the PP population as a robustness check using only observed data. Any differences in interpretation of the results from the ITT population will be explored. For tests of no clinically significant deterioration from baseline the ITT and PP populations will be considered equally important.

Safety

The randomised safety population will consist of all patients who were randomised and took at least 1 dose of study medication. Safety data will be evaluated using actual treatment/dose received. In addition safety data from the lead-in period will be evaluated for all patients who enter the lead-in period.

The safety, ITT, and PP populations (including violations and deviations) will be determined prior to treatment unblinding.

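### For non-serious adverse events, the reporting window and lead-in denominator are wider than what the protocol collects, and no rule separates serious events in the 30-day tail that follow a start of post-study rosuvastatin

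*Protocol*

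**What the plan says.** **Analysis.** Section 6.4.2 states: "Any adverse events starting/worsening up to 30 days after the last dose of study medication will be classified as treatment emergent". The synopsis, under statistical methods, says of the randomised phase: "The latter phase will include the period up to 30 days after the last dose of study medication". Neither limits the rule to serious events. For the lead-in, section 6.3 states that "safety data from the lead-in period will be evaluated for all patients who enter the lead-in period", and the synopsis plans event frequencies in that population.

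**Collection.** Under section 4.8.1.2, all adverse events in randomised patients "should be recorded from the time a patient consents to participate in the study up until discontinuation of study treatments". For the period after that, the same section says: "Patients should be instructed to report hospitalisations and any other medically serious events that occur within 30 days after last dosing of study treatment". Section 4.8.1.3 and footnote m to Table 1 also tie the 30 days to serious events. Visit 3 at week 8 is the last visit. For screen failures, section 4.8.1.2 asks for serious events and adds: "Non-serious reports are not required for these patients".

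**After the study.** Section 3.1 states: "All patients will be offered the opportunity to continue with active commercially available therapy with rosuvastatin", once the protocol is complete. The visit 3 text makes this subject to the investigator's judgement. Sections 3.2.1 and 3.2.2 mention only active therapy that the investigator chooses. Safety data are tabulated by the treatment and dose actually received (6.3, 6.4.2); post-study drug is not mentioned.

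**The concern.** A frequency table is read as events found among the patients at risk during the stated period. If the period or the denominator is wider than the collection, missing events count as events that did not happen. This occurs twice for non-serious events: in the 30 days after the last dose, and among screen failures in the lead-in. The incidence and severity of adverse events are the stated safety objective (2.2) and safety outcome (6.2), so the printed rates are a main output of the trial.

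The tail raises a second question. It starts at about the time when every patient, placebo patients included, may be offered rosuvastatin. A serious event in a former placebo patient who has started it could be tabulated under placebo, because nothing in the protocol says how to treat it.

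**Working it through.** **1. The plan's own figure.** Section 6.5 gives 330 randomised patients and about 990 entrants at a ratio of 3:1. 330 × 3 = 990, so the figure reproduces and the ratio means entrants to randomised. Three failures per randomised patient would give 330 × 4 = 1,320, which is not the stated number.

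**2. Lead-in denominator.** Screen failures: 990 − 330 = 660, and 660/990 = 66.7% of the denominator.

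Let r be the risk of a non-serious event in patients who are later randomised, k × r the risk in screen failures, and c the share of screen failures' events that is recorded anyway. Then:

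- printed rate = r × (330 + 660 × k × c)/990
- true rate among entrants = r × (330 + 660 × k)/990
- printed/true = (1 + 2kc)/(1 + 2k)

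The documents give none of r, k or c, so these are assumptions shown over a range:

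| k | c | printed/true | understatement |
|---|---|---|---|
| 1 | 0 | 1/3 | 3-fold |
| 1 | 0.5 | 2/3 | 1.5-fold |
| 0.5 | 0 | 1/2 | 2-fold |
| any | 1 | 1 | none |

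In the worst row, a true 5% prints as 1.7%, 10% as 3.3% and 20% as 6.7%. Three-fold is the ceiling if screen failures are at no higher risk than randomised patients (k ≤ 1).

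**3. The tail.** Treatment lasts 8 weeks, or 56 days. Tail share of the window: 30/(56 + 30) = 34.9%. With the ±3-day window at visit 3 it runs from 30/(59 + 30) = 33.7% to 30/(53 + 30) = 36.1%. This is a share of days, not of events.

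| Period | Serious events | New non-serious events |
|---|---|---|
| Lead-in, later randomised | collected | collected |
| Lead-in, screen failures | collected | not required |
| On study treatment | collected | collected |
| 30 days after last dose | collected | not collected, but classed as treatment emergent |

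**4. Serious events in the tail on post-study rosuvastatin.** The documents give neither uptake nor risk. For illustration, assume uptake u of 25% to 100% among 110 placebo patients, all starting at once, and a 30-day risk q of a serious event of 0.5% to 2%. Expected events = 110 × u × q:

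- low: 110 × 0.25 × 0.005 = 0.14
- middle: 110 × 0.5 × 0.01 = 0.55
- high: 110 × 1 × 0.02 = 2.2

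The chance of at least one, 1 − (1 − uq)^110, runs from 13% to 89%. Table 1 last records concomitant medication at visit 3, so a later start has no scheduled capture.

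**The case against.** Much of the case on the other side stands.

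- **Serious events.** They are collected in screen failures and for 30 days after the last dose, so their tables do not have the collection gap. A reader might infer that all the adverse-event tables are affected; the documents do not support that.
- **The tail gap is equal across arms.** It leads to missed late non-serious events but does not by itself bias the comparison. Section 4.8.1.2 also follows existing events to resolution during the study, so some worsening may be captured. Section 6.4.2 can be read as classifying whatever is reported, without promising to look for it. Even so, the table would carry a 30-day label that its non-serious data do not support.
- **The lead-in factor is a ceiling.** Not required does not mean never recorded. Adverse events are asked about at visit 2, before the visit 2 laboratory result is known. Patients who fail on visit 1 results are withdrawn when those results arrive and may have little time at risk. The split between the two kinds of failure is not given. Lead-in events also precede study drug, so conclusions about rosuvastatin are unaffected.
- **Placebo attribution.** It is tempting to say that the tail charges rosuvastatin events to placebo and pulls the arm comparison toward no difference. The documents do not establish this. The offer depends on the investigator, uptake and start dates are not given, and tabulation by actual treatment does not say what happens to post-study drug. The safety tables are descriptive. What remains is the absence of a rule.
- **The analysis plan.** Section 6.1 promises one, and denominators and flags are often settled there. Here, though, the protocol itself fixes the window and the lead-in population, and these conflict with its own collection rules. An analysis plan that followed the protocol would inherit the conflict.

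**Conclusion.** Wrong as written, for non-serious events. Sections 6.3 and 6.4.2 and the synopsis report non-serious events over a window and a denominator that section 4.8.1.2 does not cover. About 35% of the days in the treatment-emergent window have no planned recording of new non-serious events. About two thirds of the lead-in denominator need not report them, which understates the lead-in rate by anything from nothing to three-fold. The top of that range needs no recording at all and equal risk in screen failures; the 660 rests on the protocol's planned numbers.

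The point about post-study rosuvastatin is conditional. Serious events in the tail may follow a switch from placebo to commercial rosuvastatin, and no rule identifies them. Under the assumed ranges this is about 0.1 to 2.2 events in the placebo arm: few, but noticeable if serious events are rare. It is a reason to flag such events, not evidence of a biased comparison.

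**What to change.** Reconcile sections 4.8.1.2, 6.3 and 6.4.2 and the synopsis, by changing the analysis wording:

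1. Report non-serious treatment-emergent events by arm from first dose to the end of study treatment, including those elicited at visit 3.
2. Keep the 30-day window for serious events. Flag, or show separately, those that start after post-study lipid therapy begins.
3. For lead-in frequencies, use randomised patients as the denominator for non-serious events and all entrants for serious events. List any non-serious events recorded in screen failures separately.

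Cutting every by-arm table at the last dose would be simpler. However, it would drop serious events after the last dose from the main table, and possibly events first found at visit 3 if dosing had already ended. Point 2 avoids that.

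The cost is small: a shorter stated window for non-serious events, and a start date of post-study therapy for the few patients with a serious event in the tail. No added visit is needed.

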6.5 Determination of sample size

The primary outcome variable for this study, which the sample size calculation has been based on, is the change in TG levels from baseline to Week 8.

Hypothesis testing will be undertaken to assess whether this change from baseline in TG levels is significantly different from zero (i.e., testing for a positive effect compared to baseline) for each of the rosuvastatin 10 mg and rosuvastatin 20 mg treatment groups. Similar hypothesis testing will also be performed for the placebo group.

No adjustment will be applied for the two rosuvastatin groups since the hypothesis testing in each of the treatment groups is independent. Therefore a 2-sided significance level of 5% will be applied for testing for a positive effect versus baseline. The required power is 90%.

Data taken from the literature suggest that an intervention with RSV will reduce TG levels between 22 and 25% average, with a maximum of 37% from baseline (expected p for sample 1(placebo):0.029; expected p for sample 2(RSV):0.229). We need a minimum of 67 fully evaluable patients per treatment arm to reach the 2-sided alpha 0.050 with a potency of 90% and a confident interval of 95%. Increasing sample size to 100 per arm increases potency to 97%.

As there are about 10 to15% patients that would probably not complete the 8 weeks treatment period (non-evaluable patients), we will increase the patients per treatment arm to 110 (a total of 330 randomised patients). As we have the facility of doing the trial in at least 10 centers, we can easily reach the target patients per treatment arm. Assuming a screen failure rate of 3:1 we will require approximately 990 patients to enter the study.

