4. MEASUREMENTS OF STUDY VARIABLES

4.1 **Primary variable**

The primary variable is the change TG from baseline to week 8.

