4.7 Efficacy and pharmacodynamic measurement and variables

The efficacy variables for the study are described in the table below:

Table 5	Efficacy variable(s)
Objective	Variable(s)
Primary	Percentage change in TG levels from baseline to week 8.
Secondary	
1st	Percentage change in non-HDL-C levels from baseline to week 8.
2nd	Percentage change in lipids and lipoproteins (different to TG and non-HDL-C) from baseline to week 8 (LDL-C, TC, HDL-C, ApoA1, ApoB, TC/HDL-C; LDL-C/HDL-C; nonHDL-C/HDL-C and ApoB/ApoA1 indexes)
3rd	Percent change of hsCRP from baseline to week 8.

T ce

4.7.1 **Triglycerides levels**

Triglycerides levels will be assessed from laboratory data.

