6.4 Method of statistical analysis

6.4.1 Efficacy

6.4.1.1 Triglycerides levels

The following analyses will be performed for TG:

- Last observation carried forward (LOCF) on the ITT (Intention to treat) population for primary and secondary endpoints at week 8. This will be the primary analysis.
- Observed data on the per Protocol (PP) population for primary and secondary endpoints at week 8.

Initially a Friedman analysis will be performed, then, for comparing each one of Rosuvastatin groups against placebo group at week 8 a U Man Whitney test will be done. Also, the percentage of reduction –week 8 minus basal- obtained in the placebo group will be contrasted against the percentage of reduction in each one of the Rosuvastatin groups using a U Man Whitney test. In all the cases a p < 0.05 will be considered significant.

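### Independence of the tests is no reason to skip multiplicity adjustment: two doses at 5% each carry a family error of 9 to 10%, and more if both triglyceride variables count

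*Protocol*

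**What the plan says.** Section 6.5 sets the hypothesis tests behind the sample size. For each rosuvastatin group, "Hypothesis testing will be undertaken to assess whether this change from baseline in TG levels is significantly different from zero"; and "Similar hypothesis testing will also be performed for the placebo group". It then gives the multiplicity rule and its reason: "No adjustment will be applied for the two rosuvastatin groups since the hypothesis testing in each of the treatment groups is independent". The next sentence draws the consequence: "Therefore a 2-sided significance level of 5% will be applied for testing for a positive effect versus baseline". Section 6.3 likewise treats the main test as superiority over baseline.

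Section 6.4.1.1 describes different tests. After an initial Friedman analysis, each dose is compared with placebo at week 8 by a Mann-Whitney test. In addition, the percentage reduction in the placebo group "will be contrasted against the percentage of reduction in each one of the Rosuvastatin groups using a U Man Whitney test". The threshold is the same throughout: "In all the cases a p < 0.05 will be considered significant". The synopsis adds a Wilcoxon test of week 8 against baseline inside each group.

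The primary variable is worded in two ways. Section 4.1 has "The primary variable is the change TG from baseline to week 8", and section 6.5 also speaks of change. Table 5 in section 4.7 has "Percentage change in TG levels from baseline to week 8", and section 6.2 lists the same as the one primary efficacy outcome variable. No section says which dose, variable or comparison decides whether the primary objective is met.

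**The concern.** The protocol itself fixes the no-adjustment rule and the reason for it, so this is not a detail left to the analysis plan. The reason does not support the rule. Independence describes how test statistics relate to one another; it does not limit the chance that at least one of them is falsely significant.

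Two things are at stake. First, if success on either dose counts, the chance of a false claim on the primary objective is nearly double the 5% attached to each test. Second, week-8 TG and percentage reduction are tested at the same threshold with no ranking. If they disagree, the protocol gives no basis for choosing between the two conclusions.

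**Working it through.** **Inputs from the protocol.** Two-sided 5% per test (6.5) and p < 0.05 for every test (6.4.1.1); three arms, 1:1:1, one placebo arm (3.1); expected proportions 0.029 for placebo and 0.229 for rosuvastatin, 90% power, a minimum of 67 evaluable per arm, and 110 randomised per arm with 10 to 15% non-evaluable (6.5). The protocol states no familywise error rate.

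**1. The protocol's own figure.** Two-proportion formula with p̄ = 0.129:

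n′ = [1.960·√(2·0.129·0.871) + 1.2816·√(0.029·0.971 + 0.229·0.771)]² / 0.200² = (0.9291 + 0.5798)² / 0.04 = 56.9

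With continuity correction: n = (56.9/4)·[1 + √(1 + 4/(56.9·0.200))]² = 66.6, so **67 per arm**, as stated. The same method gives 98.4% power at 100 per arm, against the stated 97%. The size therefore rests on one rosuvastatin-placebo comparison at an unadjusted 5%.

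**2. Within-arm tests versus baseline (the tests the quoted sentence concerns).** The arms hold different patients, so the tests are independent.

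- Two doses: 1 − 0.95² = **9.75%**
- Three arms: 1 − 0.95³ = **14.3%**

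**3. Dose versus placebo, percentage change only.** With equal arms, the shared placebo arm gives the two statistics a correlation of 0.5. For a bivariate normal with that correlation, P(either |z| > 1.96) = **9.1%**, slightly below the 9.75% for independent tests.

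**4. Dose versus placebo, both TG variables (four tests).** The correlation between week-8 TG and percentage change is not in the documents, so it is varied. The figures come from 2,000,000 multivariate normal draws per row, with correlation 0.5 between doses.

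| Correlation of the two variables | Family error, four tests |
|---|---|
| 0 | 17.3% |
| 0.5 | 16.2% |
| 0.7 | 14.9% |
| 0.8 | 14.0% |
| 0.9 | 12.6% |
| 1 | 9.1% |

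A direct simulation of the four Mann-Whitney tests gave **14.1 to 15.6%** (100 per arm, 10,000 trials). It used log-normal TG with baseline restricted to 200-800 mg/dL. The median of 280, log-SD of 0.4 and baseline-to-week-8 correlation of 0.3 to 0.7 are assumptions. The resulting rank correlations between the two variables were 0.58 to 0.73.

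**5. Room for an adjustment.** Evaluable patients per arm: 110·0.85 = 93.5, about 94, to 110·0.90 = 99. The formula of step 1 at 0.025 (z = 2.2414) gives n′ = 67.4 and, with continuity correction, **78 per arm**. Continuity-corrected power at 0.025 is 95.6% with 94 per arm and 96.8% with 100. The family error for the two placebo comparisons is then about 4.7%.

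**The case against.** Several points on the other side are sound.

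- **The tests in 6.5 are independent.** A reader might infer that the protocol's statement is false because both doses share a placebo arm. The text does not support that: the sentence sits among within-arm tests against baseline, and for those it is correct. The fault lies in the inference drawn from it, and in its not reaching the placebo comparisons at all.
- **The shared placebo arm is not the cause.** It lowers the two-dose figure slightly, from 9.75% to 9.1%. The number of tests drives the inflation.
- **Week-8 TG level is nowhere declared primary.** Table 5 and section 6.2 name percentage change only, and the looser wording in 4.1 and 6.5 is still about change. A flat figure near 15% would treat the level as co-primary, which no section does. What stands is that 6.4.1.1 runs both tests at the same threshold without ranking them.
- **The protocol claims 5% per test, not across the family.** Whether the two doses need joint control depends on a success rule that it does not state. If both doses had to win, there would be no inflation. However, 6.5 explicitly considers adjustment for the two doses and rejects it for an invalid reason, so the question was not left open.
- **At the expected effect the result would seldom turn on this.** Power is high with or without adjustment, which is also why correcting it is cheap.

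Nor does the opening Friedman analysis protect the later tests: the protocol does not make them conditional on its result.

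**Conclusion.** The point holds. The reason given for not adjusting is invalid for the tests it describes (9.75% for two doses, 14.3% with the placebo arm) and does not apply to the placebo comparisons (about 9.1% on the declared primary variable). These figures assume that a win on either dose, or in any arm, counts as success. The larger figure of about 14 to 16% needs two further assumptions: that week-8 TG level may also carry the claim, and that its correlation with percentage change is roughly 0.5 to 0.7. Without a figure for that correlation, the documents support only the bounds of 9.1 to 17.3%. It should be reported as conditional, not as the trial's error rate.

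**What to change.** **Primary comparison.** In the synopsis and in sections 4.1, 6.2, 6.3, 6.4.1.1 and 6.5, name percentage change in TG, each dose versus placebo, as the single primary comparison. Label the week-8 level tests and the within-arm tests against baseline as supportive. This is more than a wording change: sections 6.3 and 6.5 now make superiority over baseline the main hypothesis, and leaving that in place would create a new contradiction.

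**Error control.** Delete the independence justification. Hold the two dose comparisons jointly at a two-sided 5% by Holm or Bonferroni, or by a fixed sequence whose order is stated before unblinding.

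**Cost.** With Bonferroni, the 78 per arm in step 5 lies below the 94 to 99 evaluable patients expected, so none need be added. This takes the protocol's proportions as given. Holm rejects whenever Bonferroni does, so it costs no more. A fixed sequence splits no alpha, but the second dose cannot be claimed if the first fails. For an assumed 20-point difference and 94 per arm, that chance is 1 − Φ(20/(SD·√(2/94)) − 1.96): about 0.5% at SD 30, 2.5% at SD 35 and 14% at SD 45. The SD is not in the documents, so the choice between a sequence and Holm should rest on a sourced value.
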